The setting for our intervention was primary health care units at a rural region in Portugal, an area of 7393 km², an estimated population of 166 706 inhabitants (2011), a population density of 22.5 inhab./km², and approximately 250 GPs working in primary health care units (of which 110 were included in our study). Portugal has a public accessible national health service, but mental health indicators are alarming (28). BZD prescription in Portugal is very high, as introduced in our background section, and the consumption of these drugs is particularly significant in the region where our intervention was implemented (11).

Eligibility criteria and recruitment

All primary healthcare units from the Portuguese Central Alentejo region were considered eligible. A researcher contacted each healthcare unit coordinator, explained the project's nature, and invited to participation.

The primary inclusion criteria were healthcare units with acceptance of at least 90% of GPs to participate in the study. We chose a higher acceptance rate than usually reported in the literature since we expected, although accepting to participate in the study, a significant number of GPs in each cluster would not actively use the DBCI ePrimaPrescribe platform.

Sample size

The unit of observation for primary analysis was at the individual GP prescription level. Data collected from a previous research implemented in a similar setting (29) allowed performing estimation for sample size (SS) calculation. We started by doing an SS calculation based on all observations' independence and an effect size of 20% reduction. We obtained a total of N=58 participants, N=29 participants per study arm. To adjust for the intra-cluster correlation coefficient (30), we then calculated the design effect (Deff) expressed as:

Deff= 1+r(m-1) - where r denotes the ICC and m is the size for each cluster.

Considering an average cluster of m=5 and an ICC of 0.02, Deff=1.08.

The SS adjusted for ICC was then be given by:

N*= N(1+r (m-1)), so N*=29(1+0.02(5-1)=31.3, hence approximately 32 per study arm.

The number of clusters (k) was given by:

k= N(1+r (m-1))/m, so k=6.4≈ 7

Considering an ICC of 0.02, a 1:1 ratio of allocation of controls per intervention unit, an alpha type error of 0.05, a cluster size of 5 doctors per unit, a minimal difference 20% reduction in the number of BZD prescriptions, the study would have to include 7 clusters per study arm in order to have an 80% power.

Random allocation

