Randomization was stratified according to the organizational type of primary health care unit (UCSP vs. USF), the number of GPs per unit, the average number of appointments, and the number of patients per unit per month. We further included in our randomization criteria primary health care unit's proximity, meaning that when distinct units functioned on the same location/building, we allocated them to the same study arm.

In previous research, using similar baseline BZD prescription data from primary health care units, there was a large spread of monthly BZD prescription (29). Since this spread was similar throughout different units, no stratified randomization (or matching for similar prescribing patterns) was considered to be necessary (31).

Healthcare units were included if 90% of the GPs accept participation.

For concealment of allocation, after all eligible healthcare units accepted participation, we allocated them simultaneously to intervention or control group using a computer-generated random number of tables.

The distribution of participants after randomization is presented in the following figure.

[figure not shown]

Figure 1: Distribution of participants after randomization

Blinding

GPs could not be blinded due to the fact that they were asked to participate actively in a study seeking to change their prescription practice. Both GPs included in intervention and control arm were asked to access an online platform. However, they were blinded to the existence of alternative content to the platform presented in their primary health care unit.

The authors were not blinded to primary health care unit allocation.

The primary and secondary outcomes were assessed by analysis of the electronic prescription and diagnosis registration database for each GP. These data were extracted and anonymized (except to primary health care unit identification) by a data manager at the central Shared Services of the Portuguese Ministry of Health, who was not involved in the study and was blinded to participant allocation.

Intervention

Development of Digital Behavior Change Intervention (DBCI) online programs

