All face-to-face visits, and hence intervention procedures explanation and monitoring were provided by the first author, who has a background as a psychiatrist and regularly performs her clinical work in the same geographical area where the intervention was implemented.

We performed semi-structured in-depth interviews with an intentional sample of participants from the intervention arm to explore perceptions on the feasibility and implementation of the study.

Outcome assessment

Primary outcome measure

We used as primary outcome measure the frequency of BZD prescriptions issued per month, the proportion of prescriptions issued by participants included in intervention and control units over the study time frame and more specifically at baseline, six and 12 months after intervention.

We included BZDs from the following Anatomical Therapeutic Chemical classification system-coded groups: N05B; N05C and N03AE.

Secondary outcome measures

Effectiveness

We used the frequency of antidepressant prescriptions issued per month, the proportion of prescriptions issued by participants included in intervention and control units over the study time frame and more specifically at baseline, six and 12 months after intervention.

We included antidepressants from the following Anatomical Therapeutic Chemical classification system-coded groups: N06A.

To study the effect of ePrimaprescribe on diagnosis registration, we used the monthly registration distribution of psychological symptoms, complaints, and diagnoses coded at the same month as BZD and antidepressant prescriptions. The GP's diagnosis registration used the International Classification of Primary Care, second edition (ICPC-2) developed and updated by the World Organization of Family Doctors' (WONCA) International Classification Committee (WICC).

We further performed a cost analysis considering the monthly National Health Service spending with BZD co-payment. This cost was compared with the amount that would need to be spent to comply with needs and solutions suggested when evaluating GP's perceptions of the feasibility and implementation.

Implementation

We studied the implementation process using quantitative and qualitative methods.

Quantitative data

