Each prescription data was coded using an individual GP and patient numerical identification, in a secured and validated electronic database, directly extracted by the central Shared Services of the Portuguese Ministry of Health.

Data concerning clinical diagnosis was extracted by the same method as the prescription database. Matching of prescription and diagnosis database was

performed using the coded patient's numerical identification and prescription/diagnosis registration month.

Data obtained through questionnaires and interviews was collected after participants signing an informed consent during the initial implementation face-to-face visit.

Statistical analysis

We performed an exploratory descriptive analysis using number of prescriptions as primary measure of outcome, considering as main influencing factors the patient's age and sex, by units of intervention and control.

We performed most analysis at the level of intervention versus control clusters (so compared together the set of intervened units vs the set of control units), since the available data did not allow for the author to identify each of the participating GP, hence also not allowing to distinguish in the intervention units, which GPs were compliant with the intervention (i.e. the doctors that actually used the DBCI), from those that, although initially agreeing to participate, finally didn't use the platform.

We tested for significant differences among the baseline characteristics of the intervention and control group. We performed descriptive analysis, with continuous variables summarized using means and standard deviations for normal distributions, and by medians and the 25th and 75th percentiles for non-normal distributions.

Estimated effects were calculated by comparing number of prescriptions in the intervention and control groups at baseline, six months, and 12 months after intervention.

All analyses were performed on an 'intention-to-treat' basis (i.e., all initially enrolled GPs were included in the analysis according to the group to which they were assigned). This approach reduces the bias that may occur when participants not receiving assigned treatments are excluded from analysis.

The intervention and control groups were compared at the defined time points accounting for clustering by unit.

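### The primary comparison does not fix its form (follow-up or change) and names no baseline adjustment; adjusting one named contrast for unit baseline prescribing is a cheap improvement whose gain depends on an unstated correlation

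*Combined protocol and SAP*

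**What the plan says.** The Primary outcome measure section takes monthly BZD prescribing over the study period, "more specifically at baseline, six and 12 months after intervention", and ranks none of these time points. The Statistical analysis section describes the effect estimate in two sentences: "Estimated effects were calculated by comparing number of prescriptions in the intervention and control groups at baseline, six months, and 12 months after intervention", and "The intervention and control groups were compared at the defined time points accounting for clustering by unit". Patient age and sex are mentioned there only for an exploratory descriptive analysis. Baseline appears as one of the compared time points and in tests of baseline differences. No section names a baseline covariate, ANCOVA, a change score or a group-by-time term for the primary outcome.

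The Random allocation section lists unit type and three size measures as stratification factors. On prescribing itself it reports from earlier research that "there was a large spread of monthly BZD prescription", and continues: "Since this spread was similar throughout different units, no stratified randomization (or matching for similar prescribing patterns) was considered to be necessary".

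**The concern.** Two things are left open: which contrast is the estimated effect, and what is done about baseline prescribing.

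The reason given for not balancing on prescribing is that units resemble one another. Chance imbalance between arms, however, comes mostly from differences between GPs inside units, and it remains even when units are alike. A follow-up-only contrast keeps whatever imbalance arose. A change score subtracts all of it, which is too much when r is below 1 (taking equal variance at the two times). The two readings can also differ a good deal in power, so leaving the choice open matters. Precision is at stake, along with how the estimate behaves in a trial that happens to start unbalanced.

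**Working it through.** **The plan's own figure.** Sample size section: "Considering an average cluster of m=5 and an ICC of 0.02, Deff=1.08". 1 + 0.02 × (5 − 1) = 1.08; 29 × 1.08 = 31.32, rounded up to 32 GPs per arm; 32/5 = 6.4, rounded up to 7 units per arm. This reproduces.

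**Back-solved spread.** No mean or SD is given. For 29 per arm, 80% power and alpha 0.05 (two-sided assumed, t-test), the standardised effect is 0.749. A 20% reduction then implies CV = 0.20/0.749 = 0.267.

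**Size of chance imbalance.** SD of the baseline gap between arms = CV × √(2 × Deff/n), with n GPs per arm.
- Planned 7 × 5 per arm: 0.267 × √(2 × 1.08/35) = 6.6%. At ICC 0 it is 6.4%, so little of it comes from differences between units.
- 110 GPs, taken as 55 per arm in 7 units: m = 55/7 = 7.86, Deff = 1 + 0.02 × 6.86 = 1.137, and 0.267 × √(2 × 1.137/55) = 5.4%.

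These are upper-end values, because stratification on unit size is ignored.

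**Variance of each contrast relative to follow-up only.** Change score: 2(1 − r), which is better only above r = 0.5. Baseline-adjusted: (1 − r²)(1 + 1/(n − 4)) with n clusters in total. With 14 clusters the adjusted variance breaks even at r = √(1 − 1/1.1) = 0.30. Allowing also for the t quantile (11 rather than 12 df), the interval breaks even at r of about 0.32–0.33. With 10 clusters the variance break-even rises to √(1 − 6/7) = 0.38.

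**Simulated unit-level analyses** (bivariate normal unit means, equal cluster sizes; t on 12 df, or 11 df adjusted).

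110 GPs, 7 units per arm:

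| | Unadjusted follow-up | Adjusted, r = 0.3 | r = 0.5 | r = 0.7 | r = 0.8 |
|---|---|---|---|---|---|
| 95% CI half-width | 11.6% | 11.7% | 10.6% | 8.7% | 7.3% |
| Power, 20% effect | 92% | 92% | about 96% | 99% | >99% |

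Planned 7 units of 5 GPs per arm, power for a 20% effect:

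| | r = 0.3 | r = 0.5 | r = 0.7 | r = 0.8 |
|---|---|---|---|---|
| Follow-up only | 79% | 79% | 79% | 79% |
| Baseline-adjusted | 78% | 85–86% | 95% | 99% |
| Change score | 65% | 79% | 95% | 99% |

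Overall type I error is 5% for all three analyses.

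**Where adjustment costs something.** At r = 0 with 14 clusters it loses about 3–4 points of power. If co-located units were merged to give 10 clusters (55 GPs per arm), power at r = 0.3 is 85% adjusted against 88% unadjusted.

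**Adding unit type and one size measure.** If these predict nothing beyond baseline, 7 × 5 power is 72% at r = 0.3 and 79–80% at r = 0.5, against 79% with no adjustment at all. With 110 GPs in 7 units per arm it is 87% and 92%, against 92%. The gain at r = 0.5 disappears, and at r = 0.3 there is a loss. These losses are upper-end, because the size measure was simulated as unbalanced between arms.

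**The case against.** The strongest reply is that the benefit is conditional and may be small. No section gives r. The Discussion's remark on frequent prescription renewal makes persistent prescribing plausible but does not establish it. With 110 GPs rather than the planned 32 per arm, an unadjusted test already has about 92% power for the 20% effect. Adjustment then adds 3–4 points at r = 0.5 and nothing at r = 0.3. Below break-even, or with fewer clusters, it costs a little. All of this stands, and it is why the point is conditional and limited to one covariate. What remains is that the contrast is not named, and that the interval narrows materially if r is moderate or high.

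A reader might infer that the analysis is invalid or has inflated false positives. The documents do not support that. In the 13% of planned-size trials with a baseline gap above 10%, a follow-up-only test is falsely significant in 12% at r = 0.5. It is falsely significant in 3.9% of the rest, so 0.13 × 12% + 0.87 × 3.9% is about 5% overall. A reader might also infer that the arms were in fact unbalanced, or that standard errors lacked a small-sample correction. The plan reports no baseline results and does not say which reference distribution was used.

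The methods are written in the past tense, so prespecification may no longer be possible. That lowers the value of the change but does not remove it.

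**Conclusion.** The point holds as a cheap improvement. The form of the primary contrast is not fixed. The wording about comparing at the defined time points leans towards separate follow-up comparisons but does not exclude change from baseline. Baseline prescribing is balanced neither by the randomisation nor by any stated adjustment.

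With 110 GPs in 14 clusters, baseline adjustment would narrow the interval by about 9% at r = 0.5 (10.6/11.6), 25% at r = 0.7 (8.7/11.6) and 37% at r = 0.8 (7.3/11.6), with essentially no change at r = 0.3. This rests on an assumed range for r, the back-solved CV, two-sided sizing, an even split of the 110 GPs, and 7 units per arm; the actual number of units is not in the readable text. It should not be read as a guaranteed gain, or as a finding that the trial is underpowered without adjustment.

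**What to change.** Name one primary contrast, for example BZD prescribing at 12 months. The documents rank no time point, so 12 months is a suggestion. Adjust it for each unit's pre-intervention BZD prescribing rate only, by ANCOVA on unit-level values or an equivalent model clustered by unit. State the denominator of the rate, use a small-sample (cluster-level t) reference, and take the mean of several pre-intervention months as the covariate if they are held. Do not add unit type or size measures by default.

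No new data are needed for a single baseline: the Blinding section says unit identification was kept in the extract, and baseline is already an outcome time point. The plan's inability to identify individual GPs does not matter for a unit-level analysis. The statistical price is one cluster-level degree of freedom, a small loss if r is below about 0.3 and a larger one with fewer clusters. The practical price is a few sentences and a short analysis. If the data have already been analysed, as the past tense suggests, report it as a post hoc reanalysis beside the analysis that was done.

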Concerning our effectiveness trial, this paper describes the protocol for a cluster-randomized trial to assess, primarily, whether a Digital Behavior Change Intervention (DBCI) would have a significant effect on BZD prescription. It also describes two secondary analyses regarding antidepressant prescription trend and reporting of diagnoses registration associated to BZD prescription, hoping that the implementation of our DBCI could secondarily translate in the improvement of anxiety disorder registration and adequate treatment (with an increasing antidepressant prescription). Randomized trials are the gold standard to assess intervention effects, and cluster-randomized trials are an appropriate design when interventions need to be introduced to groups of individuals (in our case groups of GPs prescribing in the same primary health care unit), which are randomly allocated to different study arms (30,45).

We chose as delivery method a DBCI because these online interventions have the potential for low unit-cost, high reach, effective and acceptable ways to benefit individuals and society (46).

We chose to include both prescription-related outcomes and diagnosis outcomes. Regarding prescription-related outcomes, we recognize the limitation of presenting our prescription-related outcome as the frequency of prescription. In the specific case of BZDs, this limitation is minimized by the fact that, in Portugal, the prescription of BZDs cannot be placed in chronic prescriptions. This means that when a BZD prescription is issued it has to be dispensed during the next 30 days, and that each prescription might have a maximum of two boxes of drug. Hence, we considered that, since there is the need for frequent prescription renewal, the number of prescriptions issued is an adequate measure to estimate our intervention effect.

Regarding clinical diagnosis outcomes, we recognize that our data might be a fairly inexact approach, since most prescriptions are not associated with a diagnosis, and also because even when this association was found, it didn't mean that symptoms or disorders were identified at the moment of prescription. Despite this limitation, we considered relevant to report the analysis of the change in clinical diagnosis, since it might indicate significant secondary effects coming from the intervention implementation.

We recruited GPs to participation taking into account all the available characteristics that might influence our primary and secondary outcomes: sex, years of clinical experience, type of primary health care unit and previous training in mental health. We recognize as a limitation and possible bias the fact that it was the first author that was mainly responsible for implementation, and at the same time responsible for collecting data from the questionnaires and in-depth interviews. We minimized this limitation by having all data, its categorization, content and theme identification reviewed by a researcher which was not involved with data collection.

Relationship to other studies and expected contribution

The excessive BZD prescription is a reality for many countries other than Portugal. For this reason, a large body of evidence already exists, with extended research assessing the effectiveness of interventions aiming to change BZD prescription pattern. From simple methodologies, such as sending letters to long-term BZD users, to more complex ones, such as multi-step tailored interventions, most studies show limited short-term effects. Most studies also lack a more profonde understanding of the facilitators and barriers to implementation.

We consider that our trial is innovative since it presents a methodology that was carefully prepared to reach a maximum effectiveness, at minimal cost and low need for professional time, and it also has an important focus on factors influencing implementation. We also consider our research to be of particular national interest because no matter how well structured an intervention might be, if it is not accepted by the public for whom it is designed, the results are inevitably scarce and limited. When dedicating a significant effort to explore GP's perceptions over their participation experience, we expected to contribute for two important areas of knowledge. On one hand, to better understand the factors influencing the act of BZD prescription, and possibly on a larger perspective, what this prescription

means/represents in the management of mental health issues in the primary health care setting. On the other hand, in a time and setting where online interventions are becoming more common, to explore the factors influencing acceptance and practicability of our Digital Behavior Changing Intervention. Concerning specifically this mode of delivery, we also expected for our research to contribute for an in-depth exploration of perceptions, liable to be applied on other areas besides mental health and hence helping to shape digital interventions that are adjusted to what GPs want and feel motivated to comply.

Ethics and dissemination

This trial was approved by the Ethics Commission for Health of the Regional Administration of Health for Alentejo Region (Portugal) (02/2016(CES) and the Nova Medical School, Nova University Lisbon, Portugal Ethics Commission (47/2016/CEFCM). The results of this study were disseminated via peer-reviewed publications and conference presentations. All data will be available on request.

References

1. Lader M. Benzodiazepines revisited—will we ever learn? *Addiction*. 2011;106(12):2086–109.
5. Thomas RE. Benzodiazepine use and motor vehicle accidents. Systematic review of reported association. *Can Fam Physician*. 1998;44:799.

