The online programs were designed based on Behavior Changing Wheel theory (32) theory, considering that behavior change is key to improving healthcare and health outcomes. We used a Digital Behavior Change Intervention (DBCI) mode of delivery. The ePrimaPrescribe program, designed to be implemented in the intervention group, was developed based on guidelines for anxiety and depression treatment and benzodiazepines withdrawal. Our primary sources of information were National Institute for Health and Care Excellence (NICE) guidelines (33), guidelines issued by the Portuguese National Health Directorate (DGS) (34,35), and other relevant literature specifically addressing deprescribing evidence-based practice guidelines (36,37). The program comprised three e-learning modules, each with approximately 30 minutes of duration and with the following subjects: pharmacological effect and clinical use of BZD; how to treat anxiety disorder avoiding the continuous use of BZD; how to manage BZD dependence and BZD withdrawal proposals.

The primary health care units included in the control arm of our study were also offered an online platform, named ComunicaSaudeMental. This DBCI platform's content was developed based on literature concerning general communication techniques and more specific communication techniques for addressing light to moderate mental health disorders or patient's emotional management at primary health care settings. This program comprised (similarly to the one offered to the intervention arm) three e-learning modules, each with approximately 30 minutes.

After the development phase, modules were uploaded to two moodle platforms (one for the intervention educational platform, ePrimaPrescribe; another for the control educational platform, ComunicaSaudeMental), and an individual coded access was created to each participant.

Before the implementation phase, both programs were tested by three GPs and three psychiatrists. Two of the GPs were members of the Primary Health Care Research Department at NOVA Medical School, and one was also a member of the Mental Health Research Department at NOVA Medical School. Two of the three psychiatrists were specialists in substance misuse. These experts were asked to comment on the accuracy and quality of the e-learning modules critically. Their suggestions were carefully considered, and when appropriate, were integrated into the module's final version.

Intervention implementation

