We developed a standardized onsite survey aiming to explore the following themes: GP's self-evaluation of knowledge about the management of patients with anxious and depressive symptomatology; reasons for prescribing BZDs and antidepressants; subjective assessment of the amount of BZDs and antidepressants prescribed; reasons for keeping long-term BZD prescription; difficulties for changing long-term BZDs prescription; the degree of concern with continued BZD prescription; knowledge and degree of adequacy of the existing Portuguese guidelines on BZD prescription; motivations and expectations regarding the use of the ePrimaPrescribe program in clinical practice and participation in the study. This questionnaire had 18 multiple questions and 14 short answer questions. The development and testing of this questionnaire is detailed in Part 5, section 1.

We adapted the Barriers and Facilitators Assessment Instrument (BaFAI)(39) to the implementation of the DBCI ePrimaPrescribe program. This questionnaire is organized into four categories: barriers deriving from the characteristics of the practice/innovation; barriers deriving from the characteristics of the professionals; barriers due to patient characteristics; barriers arising from the intervention context. It has twenty-five questions of a five-point Likert scale type.

We asked all participating GPs to complete the onsite survey and BaFAI questionnaires at the end-of-study face-to-face visit that was performed after completion of the twelve-month intervention period.

At the end-of-study face-to-face visit, we also collected GPs sociodemographic data.

Qualitative data

During our end-of-study face-to-face visit, we performed a group discussion in each primary health care unit included in the intervention group, to explore GP's perceptions over their participation.

We finally performed semi-structured in-depth interviews with an intentional sample of participants from the intervention arm to explore perceptions of the study's feasibility and implementation. The interview guide structure was developed after an exploratory analysis of the themes emerging from the answers to the onsite survey questionnaire, from the answers to the BaFAI, and from the group discussion occurring during the end-of-study visit.

Data management

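### Review by a second researcher limits coding bias only, so response bias may remain in the implementation questionnaires that the implementer collected

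*Combined protocol and SAP*

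**What the plan says.** The section on intervention implementation states: "All face-to-face visits, and hence intervention procedures explanation and monitoring were provided by the first author". It adds that this person is a psychiatrist who "regularly performs her clinical work in the same geographical area where the intervention was implemented".

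Under Quantitative data, GPs are asked to "complete the onsite survey and BaFAI questionnaires at the end-of-study face-to-face visit". The survey has 18 multiple questions and 14 short-answer questions. BaFAI has 25 five-point items. Under Qualitative data, a group discussion takes place at the same visit in the intervention units, and interviews with a purposive sample follow.

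The Discussion (Strengths and limitations) discloses the problem: "We recognize as a limitation and possible bias the fact that it was the first author that was mainly responsible for implementation". The same sentence makes clear that this person also gathered the questionnaire and interview data. The only stated remedy comes next: "We minimized this limitation by having all data, its categorization, content and theme identification reviewed by a researcher". That second researcher is described as having had no part in gathering the data. The documents describe no safeguard at the point of collection, such as a separate administrator or a sealed return.

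**The concern.** Two kinds of bias can follow when the person who promotes a programme also collects opinions about it. The collector may code or interpret answers in the programme's favour. Separately, respondents may give that person a different answer from the one they would give someone else. A later independent reading addresses the first kind. It has no access to the second.

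The survey is open to the second kind. It asks GPs to rate their own knowledge, say how much BZD they think they prescribe, explain why long-term prescriptions continue, and state their motivation to use the programme. The person collecting the answers is a local psychiatrist who introduced that programme to them.

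The implementation results are meant to show what helps and hinders use, and the Discussion presents this as a main contribution of the trial. The eligibility section expects many GPs in each cluster not to use the platform actively. The Statistical analysis section says the available data could not separate users from non-users. Self-report is therefore the main described source on why GPs did not use it. A reader told that the bias was minimised may rely on these answers more than the safeguard allows.

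**Working it through.** The plan states no figure for this point, so the check compares its sections.

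**1. Who collected the data.** The implementation section has one person making all visits. The Quantitative data section places both questionnaires at the last of those visits. The Discussion confirms that the same person collected questionnaires and interviews. The dual role is stated in the documents, not inferred.

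**2. What the review can act on.** I read the survey's multiple questions as closed items.

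| Data | Items | Correctable by later review | Not correctable by later review |
|---|---|---|---|
| BaFAI, five-point | 25 | Entry errors | The point the GP chose |
| Survey, multiple questions | 18 | Entry errors | The option the GP chose |
| Survey, short answers | 14 | Categorisation | What the GP chose to write |
| Discussions and interviews | n/a | Themes, interpretation | What was said or withheld |

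Closed items: 25 + 18 = 43. All questionnaire items: 43 + 14 = 57. So 43/57, about 75%, are closed items with almost nothing to categorise. The review has real value for the short answers and the qualitative material, and very little for the rest.

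**3. Effect on a shifted answer.** Write recorded answer = answer the GP would give a neutral collector + shift. The review sees only the recorded answer. As an assumption not found in the documents, suppose a share f of GPs move one point in the same direction on a five-point item. The item mean then moves by f × 1: 0.1, 0.2 or 0.3 points for f = 10%, 20% or 30%. The review removes none of this, whatever the sign, and more respondents do not reduce it. This shows the mechanism only. The Statistical analysis section plans chi-squared associations with sociodemographic characteristics, not tests of item means.

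**4. Direction.** A wish to please points towards favourable answers. However, BaFAI also covers barriers attributed to the innovation, the patients and the context. A GP who did not use the platform could save face by blaming these, which would overstate barriers. The documents do not settle which effect dominates.

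**5. Reach.**
- The onsite survey and BaFAI are exposed.
- The interview guide is built partly from those answers, so influence can carry forward.
- The cost outcome compares BZD co-payment spending with the cost of solutions that GPs suggest. That side of the comparison rests on their perceptions.
- Prescription and diagnosis outcomes come from an electronic database, extracted by an uninvolved data manager blinded to allocation (Blinding section). They are outside this point.

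**The case against.** The best defence is that the authors disclose the dual role themselves, in a limitations paragraph, for both questionnaires and interviews. What is left is largely one verb. That stands as credit to the authors, but the verb still claims more than the remedy delivers for closed items.

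The mode of completion is not fully known. The wording is compatible with self-completion, and the survey's development is referred to a part of the work not in this document. A reader might infer that no safeguard was used; the documents show only that none is described.

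A reader might also infer that barriers will be understated and acceptability overstated. The documents give no direction, and face-saving by non-users could act the other way. Nor do they support reading the dual role, through these questionnaires, as a threat to the prescribing results, which do not depend on GPs' answers.

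The document is written mostly in the past tense, so collection may be over and only a wording change possible. That limits the fix but not the point.

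Finally, a coded form is not anonymous, and the access codes were handed over at visits the implementer made, so some wish to please could survive. This is a fair limit on what the fix can achieve.

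**Conclusion.** The concern holds in a limited form and is minor. Review by a researcher outside data collection can limit coding and interpretation bias. It cannot correct response bias, so the statement that the limitation was minimised is not supported for the closed self-report items. Response bias may remain, plausibly but not certainly in the favourable direction. Its size cannot be derived from the documents. The effect is confined to one secondary objective (the implementation process) and to the perception-based side of the cost comparison. The conclusion assumes that the review worked only on data already collected, as the description implies, and that no unreported safeguard operated at the visit.

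**What to change.** **If collection is still to come.**
- At the end-of-study visit, have GPs complete the survey and BaFAI themselves, on paper, under a study code, and return them in a sealed envelope.
- Have the second researcher open the envelopes and enter the data.
- Tell GPs beforehand that the implementer will not see individual answers.
- Give the implementer only pooled summaries for building the interview guide.
- Put the same code on the sociodemographic form, so that the planned cross-tabulations remain possible.

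An online form on the study platform would be a poorer choice, even though "an individual coded access was created to each participant": GPs who never used the platform would have to log in to it to say why.

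**In either case.** In Strengths and limitations, replace the claim of minimisation with a statement that the second researcher's review limits coding bias only, and that response bias of unknown size and direction remains. If collection is complete, make this change and report that the implementer collected the questionnaires.

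**Cost.** Envelopes, some data-entry work for the second researcher, a few more blank items, and no clarification on the spot. Group discussions and interviews are unchanged, so response bias there is not reduced. The wording change is free.
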